## **11.2 Premature termination of the clinical study**

According to the German Fachinformation for Simvastatin, the combined incidence for myopathy/rhabdomyolysis in 41.413 patients treated for at least 4 years was 0.08% for 40mg/d Simvastatin. Severe symptomatic hyponatremia (serum sodium [ $S_{Na}$ ]  $<125$  mmol/L) is a rare but potentially fatal complication of Escitalopram. Signs and symptoms of hyponatremia include headache, difficulty concentrating, memory impairment, confusion, weakness, and unsteadiness and can be as severe as hallucination, syncope, seizure, coma, respiratory arrest, and death. Therefore, the whole study may be discontinued at the occurrence of the treatment-related serious adverse event (SAE) “myopathy/rhabdomyolysis” as defined by the German Fachinformation for Simvastatin [muscle pain, tenderness or weakness with creatine kinase (CK) above ten times the upper limit of normal (ULN)] in more than 5 participants or the treatment-related SAE “severe symptomatic hyponatremia” (serum sodium [ $S_{Na}$ ]  $<125$  mmol/L) in more than 5 participants. In addition, an early discontinuation of the trial may be decided if new scientific data during the course of the trial changes the risk-benefit-balance significantly. If such data emerges, recruitment and treatment of currently treated patients will be paused immediately. A final decision on continuation or termination of the trial will then be made by the Sponsor/PI based on the recommendation of the Data and Safety Monitoring Board (DSMB).

### **11.3 Follow-up and continuing treatment after regular / premature termination**

After completing all the protocol treatment and visits, patients will continue with regular visits according to usual practice. In case of response or remission, Escitalopram will be continued while the study medication Simvastatin (IMP) will be discontinued in any event.

In case of non-response or non-remission, Escitalopram will be definitely discontinued. The investigator will ensure a gradual dose reduction of Escitalopram over at least one or two weeks because of potential symptoms associated with abrupt discontinuation of Escitalopram. Patients with non-response or non-remission will be offered at least one additional clinical appointment at the psychiatric outpatient clinic of the study center after termination of the individual study participation for the gradual discontinuation of Escitalopram.

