### 5.2.1 Secondary efficacy (exploratory) endpoints

As secondary outcome variables we will use

- MADRS response (defined as 50% MADRS score reduction from baseline),
- MADRS remission (defined as MADRS score < 10), and
- MADRS minimal clinically important difference (MCID).

The MCID concept originated from studies of patient-reported outcomes, in which it represented the smallest improvement that was considered meaningful by the patient [57]. Empirically, the MCID using the MADRS has been identified as a change from baseline between 1.6 – 1.9 [58].

Also, we will assess as secondary outcome variables

- change scores in patients' self-reported Beck Depression Inventory (BDI-II) as well as
- the MCID according to BDI [59]

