### 5.2.2 Other secondary (exploratory) endpoints

We will additionally determine

- The clinician's impression of the severity of illness (Clinical Global Impression scale – Severity of illness, CGI-S) [60],
- the clinician's impression whether and to what extent symptoms have improved (Clinical Global Impression scale – Improvement, CGI-I) [60],
- the patient's impression whether and to what extent symptoms have improved (Patients' Global Impression of Change Scale, PGIC),
- social functioning (Social and Occupational Functioning Assessment Scale, SOFAS),
- quality of life (EuroQol-5 Dimensions-3 Levels Questionnaire, with a calculated MCID [61]),
- change scores in high-density lipoprotein (HDL), low-density lipoprotein (LDL), and total cholesterol,
- and change scores in mitochondrial function (spare respiratory capacity) of immune cells and indicators of immune function.

Please see Table 1 for characteristics and definitions of primary and secondary outcome variables.

**Table 1:** Characteristics and definitions of primary and secondary endpoints.

Outcome	Instrument	Rating	Domain	Exactly defined outcome	Variable
Primary	MADRS	Clinician-rated	Severity of Depression	Mean Change from Baseline	Continuous

Secondary / Efficacy (exploratory)	MADRS	Clinician-rated	Severity of Depression	- Percentage response (>50 % reduction from baseline) - Percentage remission (MADRS score < 10 post-treatment) - Percentage minimal clinically important difference (MCID; change from baseline score > 1.9)	Dichotomous
Secondary / Efficacy (exploratory)	BDI-II	Self-rated	Severity of Depression	Mean Change from Baseline - Percentage MCID (> 17.5% change from baseline)	Continuous Dichotomous
Secondary Exploratory	CGI-S	Clinician-rated	Severity of illness	Median Change from Baseline	Ordinal
Secondary Exploratory	CGI-I	Clinician-rated	Improvement/worsening of illness	Response defined as "much improved" or "very much improved" post-treatment	Dichotomous
Secondary Exploratory	PGIC	Self-rated	Subjective Improvement	Response defined as "much improved" or "very much improved" post-treatment	Dichotomous
Secondary Exploratory	SOFAS	Clinician-rated	Social Functioning	Mean Change from Baseline	Continuous
Secondary Exploratory	EQ-5D-3L	Self-rated	Quality of Life	Mean Change from Baseline Percentage MCID (change from baseline score > 0.74)	Continuous Dichotomous
Secondary Exploratory	HDL, LDL, total cholesterol	Laboratory values	Metabolism	Mean Change from Baseline	Continuous

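### Sections 11.3 and 20.2 literally order Escitalopram both continued and stopped in a patient who responds without remitting

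*Combined protocol and SAP*

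**What the plan says.** Section 11.3 of the combined protocol and SAP gives two drug rules in consecutive paragraphs, and section 20.2 repeats both:

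- Continue: "In case of response or remission, Escitalopram will be continued while the study medication Simvastatin (IMP) will be discontinued in any event".
- Stop: "In case of non-response or non-remission, Escitalopram will be definitely discontinued".

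Two supporting sentences follow the stop rule: "The investigator will ensure a gradual dose reduction of Escitalopram over at least one or two weeks", and "Patients with non-response or non-remission will be offered at least one additional clinical appointment". The appointment sentence uses the same pairing as the stop rule.

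Neither section names a scale. Elsewhere the protocol treats response and remission as separate outcomes:

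- Section 5.2.1, response: "MADRS response (defined as 50% MADRS score reduction from baseline".
- Section 5.2.1, remission: a MADRS score below 10.
- Table 1 in section 5.2.2, response: "Percentage response (>50 % reduction from baseline".

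Table 1 also defines a response on the CGI-I and on the PGIC.

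**The concern.** The two rules are set out as opposites, but the negation is wrong. The opposite of *A or B* is *neither A nor B*; the protocol writes *not A or not B*. Anyone who meets exactly one of the two outcomes is therefore covered by both rules.

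The main group is responders with residual symptoms. Read literally, the protocol makes stopping an antidepressant mandatory in a patient whose score has halved, directly after saying that the drug is continued. Simvastatin stops in every case, and the synopsis lists no follow-up. A responder taken off Escitalopram on the literal stop rule would thus lose both drugs, with no further trial visit planned. Section 6.1 foresees 8 centers, and they could handle the same patient in opposite ways.

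**Working it through.** The plan gives no figure to reproduce here. The check is logical, with one worked score as illustration.

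**Step 1: the rules.** Let A be response and B remission. The continue rule applies when A or B holds. The stop rule, as written, applies when A fails or B fails, which means whenever A and B do not both hold.

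| Response | Remission | Continue rule | Stop rule as written | Stop rule with *neither* |
|---|---|---|---|---|
| yes | yes | applies | – | – |
| yes | no | applies | applies | – |
| no | yes | applies | applies | – |
| no | no | – | applies | applies |

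As written, the two middle rows fall under both rules. With *neither response nor remission*, each row falls under exactly one.

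**Step 2: can the middle rows occur?** Inputs are the MADRS definitions in sections 5.2.1 and 5.2.2 (Table 1), and the entry threshold of 18 or more in section 6.2.1. Applying MADRS is an inference, since 11.3 and 20.2 name no scale.

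- Example, baseline 30 and week 12 score 14: the reduction is (30 − 14)/30 = 16/30 = 53.3%, a response under both 5.2.1 and Table 1. The score 14 is not below 10, so there is no remission. Both rules apply.
- Range at baseline 30: scores 10 to 15 conflict if response means at least 50%, and scores 10 to 14 if it means more than 50%.
- Lowest baseline at which a responder can miss remission: 20 under at least 50% (20 to 10 is exactly 50%), and 21 under more than 50% (21 to 10 is 11/21 = 52.4%).
- Remission without response, at baselines of 18 or more: impossible under at least 50%, because a score of 9 or less is always at most half of 18 or more. Under more than 50% there is one case, 18 to 9, which is exactly 50%.

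These are possible scores, not patient counts.

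**Step 3: does anything else settle it?** The statements against stopping effective medication (sections 6.2.1, 7.2.2 and 8) concern qualifying for the study, not what happens after it. The reference to usual practice in 11.3 is about visits: "patients will continue with regular visits according to usual practice". Neither decides the drug rule.

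**Step 4: number of patients.** This would need the share of patients with exactly one outcome at week 12. The documents give no expected baseline mean, response rate or remission rate, so no number follows.

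**The case against.** The strongest reply is that this is a slip with an obvious meaning. The sentences are plainly meant as opposites. If the literal stop rule prevailed, only patients with both outcomes would continue, and the *or* in the continue rule would have no effect. Reading the stop rule as *neither* leaves the continue rule intact. That stands as good evidence of intent.

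It does not make the text safe to follow. Stopping the drug in everyone short of remission is also a coherent policy, the stop rule is worded as mandatory, and the same pairing returns in the appointment sentence.

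It is also fair to say that the harm is limited. The protocol requires a taper and offers a further appointment, regular care continues, and Escitalopram is a readily available generic. All of this stands, and it keeps the point small.

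A third reply is that MADRS endpoint definitions are being brought into a paragraph about care. That is true of the worked scores. The overlap itself needs no scale: it exists wherever response and remission can differ.

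Two stronger readings are tempting. A reader might infer that the sponsor chose to withdraw an effective drug from responders; the continue sentence says the opposite. A reader might also infer that trial results are affected or that many patients are at risk; no endpoint, sample size or analysis in the plan uses this rule, and no patient number can be derived.

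**Conclusion.** The point holds as a wording error in a mandatory drug instruction. In sections 11.3 and 20.2 the stop condition is not the complement of the continue condition, so a patient who responds without remitting is literally under both orders. The likely intent is to stop only when there is neither response nor remission.

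The effect is on post-study care and on consistency between sites. Endpoints, type I error, power and analyses do not change. The number of patients affected is unknown and cannot be estimated from the documents.

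The conclusion rests on two assumptions. First, response and remission are distinct states, as section 5.2 and Table 1 define them. Second, the rule is applied once study participation is over. The body of 11.3 starts from completed treatment and visits, although its heading also mentions premature termination. The text should be corrected because the instruction is wrong as it stands and the repair costs almost nothing.

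**What to change.** In both 11.3 and 20.2:

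1. Replace *non-response or non-remission* with *neither response nor remission* in the stop sentence and in the extra-appointment sentence.
2. Add to the continue sentence: *unless Escitalopram was stopped for safety reasons (see 11.1)*. The heading of 11.3 mentions premature termination, and 11.1 lists discontinuation reasons such as QTc prolongation, serotonin syndrome and mania. An unconditional instruction to continue should not reach those patients.
3. Naming a scale is optional, since the repair works without one. If one is named, use the protocol's MADRS definitions, and first reconcile 50% in section 5.2.1 with more than 50% in Table 1.

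The cost is rewording three sentences in each of two sections, with no effect on data collection or analysis. Reconciling the response definition is extra wording, needed only if a scale is named.

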## **12. Adverse events**

### **12.1 Definitions**

#### *12.1.1 Adverse Event (AE)*

An adverse event is an untoward medical occurrence in a patient or clinical trial subject administered a medicinal product and which does not necessarily have a causal relationship with this treatment. An AE could be diseases, signs or symptoms which occur or worsen after enrolment of the patient in the clinical trial.

#### *12.1.2 Adverse Reactions (AR)*

Adverse reactions are all untoward and unintended responses to an investigational medicinal product related to any dose administered.

#### *12.1.3 Serious Adverse Event (SAE) / Serious Adverse Reaction (SAR)*

A serious adverse event or serious adverse reaction is an untoward medical occurrence or effect that at any dose

- results in death,
- is life-threatening,
- requires hospitalisation or prolongation of existing hospitalisation,
- results in persistent or significant disability or incapacity,
- or is a congenital anomaly or birth defect;
- requires a higher benzodiazepine regimen or prescription of antipsychotics (“rescue medication”).

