## 8. Concomitant medication / concomitant therapy

Medication that is contraindicated with Simvastatin, and Escitalopram will not be permitted (see 7.2.5).

- Use of potent CYP3A4-inhibitors (e.g. clarithromycin, erythromycin, HIV protease inhibitors).
- Use of potent CYP3A4 inducers (carbamazepine, efavirenz, nevirapin, etravirine).
- Medication that is associated with QTc-prolongation [antiarrhythmica class IA and III, antipsychotics (e.g. haloperidol), phenothiazines, tricyclic antidepressants, antibiotics (e.g. moxifloxacin), and certain antihistaminergic drugs (e.g. astemizol, mizolastin)].
- Use of nonselective, irreversible monoamine oxidase inhibitor (e.g. Tranylcypromine) or selective, reversible inhibitor of monoamine oxidase A (e.g. Moclobemide) or the nonselective, reversible monoamine oxidase inhibitor Linezolid.

Concomitant treatment with antidepressants other than Escitalopram will not be permitted. In case of current treatment with antidepressants at study entry a wash-out of prior antidepressants for at least 7 drug-free days prior to inclusion may be permitted. However, discontinuation of effective medication to enable study participation is prohibited.

Other psychotropic drugs (including antipsychotics, anticonvulsants, lithium, or St. John's Wort) are not permitted during the study period with the following exceptions.

- In case of sleep difficulties, benzodiazepine or nonbenzodiazepine hypnotics (e.g. zolpidem, zopiclone) will be allowed on an "as needed basis".
- In case of acute anxiety or agitation, a benzodiazepine (preferably lorazepam) may be prescribed not exceeding 3 mg/d (other benzodiazepines at the equivalent dosage).
- Opiates for pain relief.

Any clinical exacerbation requiring a higher benzodiazepine regimen or prescription of antipsychotics ("rescue medication") will be considered as a serious adverse event.

In case of non-psychotropic medication stable pharmacological medication for at least 14 days prior to study entry will be permitted. Patients with any changes in medication dose or frequency of therapy during the 14 days prior to study entry will not participate in the study (see 6.2.1). Concomitant use of statins will not be permitted.

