### *12.3.2 Assessment of causality*

To assess causality between administration of the IMP and the Adverse Event the following definitions apply:

Sure: The reaction comprehensively follows the administration of the IMP in the right timeframe or can be measured in body tissues or fluids or represents a known or expected response to the study medication or disappears after discontinuation or dose reduction and reoccurs after re-exposure.

Probable: The reaction comprehensively follows the application of the IMP in the right timeframe or represents a known or expected response to the study medication or disappears after discontinuation or dose reduction and cannot be explained by known characteristics of the patient's disease.

Possible: The reaction comprehensively follows the application of the IMP in the right timeframe or represents a known or expected response to the study medication, but could easily be caused by other factors.

Not related: Adequate Information supporting the assumption that there is no causality

Cannot be evaluated: The causality cannot be determined.

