## **12.7 Data Monitoring Committee**

We will seek advice from independent experts in the field who have agreed to serve on the Data and Safety Monitoring Board (DSMB):

- [name]. [name] (methods expert/epidemiologist), Vrije Universiteit Amsterdam

- [name]. [name] (clinician), Zentralinstitut für Seelische Gesundheit, Mannheim
- [name]. [name] (clinician), Klinik für Psychosomatik und Psychotherapeutische Medizin Universitätsmedizin Rostock
- [name] (patient representative), Deutsche Depressionsliga

To ensure that the patients' perspective will be present at all DSMB meetings as recommended by the European Patient Academy [77], [name], vice-chair of the "Deutsche Depressionsliga" has kindly agreed to serve on the DSMB. The DSMB will regularly (once a year) assess safety data during the course of this study and their primary interest is the safety of study participants and integrity and validity of collected data.

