### **16.5 Analysis of adverse events**

All adverse events (AE; any undesirable experience occurring to a participant during the trial, whether or not considered related to the study medication) reported by the subject or observed by the investigators will be recorded at each visit. Standard procedures for reporting of (serious) adverse events will be used. (Serious) adverse events will be summarized as frequencies and percentages by treatment group. For recurrent events and to account for variable follow-up times event rates will be reported with rate ratios comparing Simvastatin with add-on placebo control and 95% confidence intervals. We will use Poisson regression models with adjustment for over dispersion (or negative binomial regression models) with offset for follow-up time and possibly a mixture component to account for zero-inflation. For events of particular interest Kaplan-Meier curves stratified by treatment group will be computed and compared by log-rank tests.

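### Needing rescue medication counts as an SAE and 16.5 does not separate these events, so the overall SAE comparison between arms mixes antidepressant benefit with harm

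*Combined protocol and SAP*

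**What the plan says.** Section 12.1.3 lists six criteria for a serious adverse event or reaction. Beside death, threat to life, hospitalisation, disability and congenital anomaly stands an event that "requires a higher benzodiazepine regimen or prescription of antipsychotics". Section 8 gives the trigger: "Any clinical exacerbation requiring a higher benzodiazepine regimen or prescription of antipsychotics" is to be treated as an SAE. Benzodiazepines and hypnotics within the limits of section 8 do not count.

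Section 16.5 summarises adverse and serious adverse events by treatment group as counts and percentages. For recurrent events and unequal follow-up it adds that "event rates will be reported with rate ratios comparing Simvastatin with add-on placebo control and 95% confidence intervals". It has no category, exclusion or sensitivity analysis for SAEs that qualify only through rescue use. Table 1 (section 5.2.2) does not list rescue use among the endpoints.

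Other safety provisions are present:

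- Section 12.3.2 has each event rated for causality ("To assess causality between administration of the IMP and the Adverse Event the following definitions apply").
- Section 16.5 says: "For events of particular interest Kaplan-Meier curves stratified by treatment group will be computed". It does not name those events.
- Section 11.2 ties possible discontinuation of the trial to counts of two named treatment-related SAEs, myopathy/rhabdomyolysis and severe symptomatic hyponatremia.
- Section 12.7 states: "The DSMB will regularly (once a year) assess safety data during the course of this study".
- Section 16.4 leaves analysis details to a statistical analysis plan to be completed before database lock and unblinding.

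**The concern.** In a depression trial, a clinical exacerbation that needs rescue is in good part the disease under study getting worse. If the primary hypothesis in 16.1.1 is true, placebo patients can be expected to need rescue more often, and each such event adds an SAE to the placebo arm. The overall SAE comparison then tilts in favour of Simvastatin exactly when the drug works and its safety profile matters most. If Simvastatin does not change rescue need, the same number of extra events falls in both arms and pulls the ratio towards 1. In either case a reader of the overall SAE line cannot tell how much of it is benefit and how much is harm.

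**Working it through.** **Inputs from the documents.** Allocation is 1:1 (7.2.7). Section 16.2 plans 64 patients per group for 80% power at d = 0.5 and a two-sided 5% level, and 80 per group after 20% dropout. These figures reproduce: the exact two-sample t-test needs 63.8, so 64, with power 0.801; 64 / (1 − 0.20) = 80. The denominator of each SAE percentage is therefore about 80.

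**Inputs that are assumptions.** The documents state no expected SAE rate and no expected rescue rate. Let h be the risk of an SAE that is serious for another reason, and r the risk of a rescue-only SAE, with the two independent within an arm. Then

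risk of any SAE = 1 − (1 − h)(1 − r).

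Take h = 2.5% on placebo and 5% on Simvastatin, a true ratio of 2.0 (2 against 4 expected patients out of 80). Vary placebo rescue from 2% to 20%, and let Simvastatin leave it unchanged, multiply it by 0.75, or halve it.

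*Worked cell, 10% halved to 5%.* Placebo: 1 − 0.975 × 0.90 = 0.1225, or 9.8 of 80. Simvastatin: 1 − 0.95 × 0.95 = 0.0975, or 7.8 of 80. Ratio 0.80.

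*Worked cell, 2% in both arms.* Placebo: 1 − 0.975 × 0.98 = 0.0445. Simvastatin: 1 − 0.95 × 0.98 = 0.0690. Ratio 1.55.

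Apparent ratio of patients with any SAE, when the true non-rescue ratio is 2.0:

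| Placebo rescue | unchanged | × 0.75 | × 0.5 |
|---|---|---|---|
| 2% | 1.55 | 1.44 | 1.34 |
| 5% | 1.32 | 1.16 | 1.00 |
| 10% | 1.18 | 0.99 | 0.80 |
| 20% | 1.09 | 0.88 | 0.66 |

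**Second model as a check.** Use non-overlapping events and h = 3% against 6%, again a true ratio of 2.0:

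- rescue 2% in both arms: (6 + 2)/(3 + 2) = 1.60
- rescue 2% against 1%: (6 + 1)/(3 + 2) = 1.40
- rescue 6% in both arms: (6 + 6)/(3 + 6) = 1.33
- rescue 6% against 3%: (6 + 3)/(3 + 6) = 1.00
- rescue 12% against 6%: (6 + 6)/(3 + 12) = 0.80

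Across both models the apparent ratio runs from 0.66 to 1.60. With no effect on rescue it is diluted but stays above 1. It reaches or crosses 1 only when Simvastatin reduces rescue enough to offset the excess harm.

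**What an observer would see with 80 per arm.** For the doubling (2.5% against 5%), the chance of counting more SAE patients on Simvastatin than on placebo is 0.73 with rescue-only events left out. It is 0.62 with 10% rescue in both arms and 0.26 if 10% is halved. For a four-fold excess (2.5% against 10%), the ratio of 4.0 becomes 1.55 with 10% rescue in both arms, 1.18 with 10% halved and 0.86 with 20% halved. Fisher-test power to detect that excess is 37% with the events separated, 16% with 10% rescue in both arms and 4% with 10% halved.

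These are ratios of patient percentages. A rate ratio with a follow-up offset is pulled in the same direction, but its exact value would differ.

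**The case against.** The strongest reply is that rescue is not simply lack of efficacy. Section 7.2.5 lists depression (frequency not known) and insomnia (very rarely) among the adverse effects of Simvastatin. For Escitalopram, which both arms receive, it lists anxiety, restlessness, agitation, panic attacks, suicidality and akathisia. Section 8 speaks of clinical exacerbation in general. A rescue-only SAE may therefore be a psychiatric adverse reaction. This stands. A reader might infer that rescue-only events should be removed from the main SAE comparison and relabelled as efficacy; the documents do not support that, since it would risk moving psychiatric harm out of the safety table.

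A second reply is that only the all-SAE aggregate is touched. CK and transaminases are measured at five visits (9.6.2), individual discontinuation has its own thresholds (11.1), the stopping rule counts named events (11.2), and an analysis of myopathy contains no rescue-only events. This also stands, and it limits the scope of the point.

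Third, 16.5 does not say that one pooled SAE rate ratio will carry the safety conclusion, all safety analyses are exploratory, and the later SAP could add the split. That is fair, but nothing in the documents provides the split, and the overall SAE percentage by arm is planned. Causality ratings and the yearly DSMB review do not separate the events in that table.

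Fourth, the overall comparison detects harm poorly even when separated (37% power for a four-fold excess). True. The gain is in interpretation more than in power.

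**Conclusion.** The point holds for the overall SAE percentage by arm and for any pooled SAE rate ratio. As planned, both combine an efficacy-related component with harm. A true ratio of 2.0 for non-rescue SAEs would show as about 0.66 to 1.6 under placebo rescue rates of 2% to 20% and a Simvastatin effect on rescue between none and a halving. All of these rates are assumptions. With rescue rarer than 2% the distortion shrinks and the ratio approaches 2.0.

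Two stronger readings should be resisted. One is that the plan would hide a Simvastatin safety signal in general: named events, laboratory monitoring and the stopping rule do not use the total SAE count. The other is that reversal below 1 is to be expected: it needs both a sizeable rescue rate and a real reduction by Simvastatin, and the documents give neither figure.

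The split does not isolate drug harm completely. Hospitalisation for worsening depression remains an SAE under the ordinary criteria and would still mix the two. This is an inexpensive improvement to the reporting of safety; the primary analysis does not depend on it.

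**What to change.** Leave the rescue rule and the SAE reporting duty unchanged. Then:

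1. Flag each SAE that is serious only by the rescue criterion. The SAE form is not among the documents; if it already records which criterion made the event serious, the flag can be derived from it.
2. In 16.5 or the SAP, before unblinding, specify that SAE frequencies and rate ratios are reported both including and excluding the flagged events, with neither version replacing the other.
3. Show rescue-only SAEs by arm in their own row, with event type and causality, so that readers can judge whether they look like lack of benefit or psychiatric harm.

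The cost is one data flag and a few extra table rows. Patient care and reporting timelines do not change.
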